**Recruitment.** Pilot: Pilot participants will be recruited using the University of Houston's (UH) online research management system (SONA). Pilot participants will meet study inclusion and exclusion criteria. RCT: Our experience in recruiting participants for similar studies suggests that we will easily be able to enroll 130 participants over a 60-week period (average of 2-3 participants per week). The projected enrollment is highly feasible based on prior experience with in-person PFIIs, which yielded 2-10 participants per week. To further illustrate, [name] and Health Research Laboratory-Substance Use Treatment Clinic (AHRL-SUTC) currently receives approximately 70 calls per month (average contacts) from smokers interested in participating in smoking (basic and applied) research. For the present study, we expect approximately 60% of callers who complete the phone-screener to meet eligibility criteria; 50% of those individuals to complete the baseline appointment; and 95% of those to be eligible for the study. Participants will be recruited from UH (over 40,000 students) and greater Houston area (population of more than 2.1 million) through mainstream (newspaper, alternative newspapers, and weekly church bulletins) and electronic media (university listserves, Facebook, etc.), and advertisement posting in a community-based psychological service center (operated by the Department of Psychology) and student/staff medical clinic at UH; we will examine demographic differences across recruitment methods and adjust recruitment efforts if needed.

**Pilot Procedure.** Pilot participants will meet study inclusion and exclusion criteria. Interested individuals will complete an online pre-screener survey administered through SONA, UH's online research management system. Participants who meet eligibility criteria will be provided with the AHRL-SUTC contact information and instructed to contact the office to schedule an appointment. Pilot participants will provide informed consent, complete an on-line survey, receive personalized feedback, and complete an individual semi-structured interview with a trained researcher. The semi-structured interview will include questions about the personalized feedback format and content, and suggestions to improve the feedback.

Participants will also be asked to rate the relevance and usefulness of the feedback, and research staff will solicit suggestions for coping strategies. As in our past treatment development work, we will employ a standardized decision-making format wherein we will only proceed with item content if it is rated above a 7 on a 0 (none) - 10 (extreme) Likert-based scale for relevance and usefulness. This evaluation process will help ensure that we solicit a wide range of feedback and cut feedback that does not achieve a moderate or greater level of relevance/ usefulness for ratings. Participants will receive course credit for participating in the Pilot that will take approximately 90 minutes. Semi-structured interviews will be audio-recorded and transcribed. An independent research assistant and I will code the transcriptions across emergent themes. Data will be analyzed using the grounded theory method. Findings from these analyses, and the content ratings, will inform revisions.

**RCT Procedure.** Upon arrival, participants will meet with a trained researcher who will obtain informed consent. The participant will then complete a 30 minutes pre-intervention online survey; an estimate derived from past work. After completing the pre-intervention survey, the participant will complete a CO assessment and provide saliva for cotinine analysis to confirm smoking status. Participants will then have a 5-minute break during which time the trained research assistant will evaluate eligibility criteria. Participants who do not meet eligibility criteria will be provided the National Cancer Institute's Clearing the Air (CTA) pamphlet, compensated

\$10, and dismissed. Participants who meet eligibility criteria will complete a 30 minutes computer-delivered intervention. Based on permuted block randomization by gender, the participant will complete either the (a) PFI or (b) smoking information control. After completing the intervention and another 5-minute break, participants will complete a 15-minute post-intervention assessment and receive a printed copy of the intervention materials. The post-intervention assessment will include manipulation check items. After completing all aspects of the baseline appointment, participants will be compensated \$20 and scheduled for their 1-month follow-up. The follow-up appointment will be completed at the AHRL-SUTC and will consist of an online survey, CO collection and, if they report being abstinent for at least 7 days prior to the appointment, saliva cotinine. This appointment will take approximately 30 minutes and participants will be compensated \$20. Participants who are unable to complete the survey at the AHRL-SUTC will have the option to complete the survey remotely and have their payment mailed or schedule a time to pick it up. Although we are aware that cotinine may be incompletely metabolized without two-weeks of abstinence, this approach (CO and cotinine) is the scientific standard to document and biochemically verify smoking status.

**Personalized Feedback Integrated Intervention.** The PFI will be modeled from those that have focused on substance use and targeted negative mood symptoms. The PFI will provide brief personalized feedback that delivers salient points on patterns of use, norms comparisons, AS, and coping strategies, and detailed text about the relation between perceived norms and behavior as well as the link between smoking and AS. First, the PFI will provide smoking feedback. Specifically, descriptive feedback on the participant's smoking behavior, history, and current nicotine dependence, perceived norms and actual norms of smoking in Texas and the US, personalized feedback on methods used to help them quit in the past and problems experienced while trying to quit in the past, feedback on money spent on smoking, health problems resulting from smoking and health benefits of quitting, perceived barriers to cessation, their smoking triggers as well as tips for quitting, managing cravings, and coping without smoking. Second, the PFI will define AS and provide information linking smoking and negative mood and the prevalence of their cooccurrence. For this portion of the PFI, participants will receive personalized feedback on smoking to cope with their negative mood, AS symptoms they endorsed, their overall AS score and a normative comparison for overall AS score among smokers, personalized feedback on rating of importance and confidence to change their AS, and coping strategies they indicated they used or were willing to use as well as additional coping strategies to help manage their AS and negative mood.

**Smoking Information Control.** Participants in the smoking information control group will receive the same computer-delivered smoking information content as the PFI condition, including smoking cessation strategies from the CTA pamphlet, but no personalized feedback or AS information. We have successfully used a similar control condition in intervention trials. The two conditions will be time matched. The use of this control will permit evaluation of personalized feedback for smoking/mood compared to non-personalized smoking content.

**Statistical Analysis Plan.** Qualitative data will be analyzed using an iterative inductive analysis method consistent with the method of grounded theory. First, the semi-structured interviews will be transcribed. Second, two independent research assistants will draft a list of recurring (e.g., discussed by 2 or more participants) themes for PFI improvements that emerge

from transcriptions. I will review all transcriptions and finalize the list of themes. Third, an independent research assistant and I will code the transcriptions across themes using Analysis Software for Word-Based Records. I will then examine the frequency of themes for the entire sample. Themes that are endorsed by at least 40% of the sample will be used to inform PFI revisions.

The primary analysis strategy will consist of examining mean differences between the intervention and control group using general linear mixed modeling and evaluating expectancies and norms as mediators of intervention effects. With respect to evaluating the main effects of experimental conditions on dependent measures, each participant will provide baseline and 1-month follow-up data. I will employ an intent-to-treat design and correct for alpha inflation using Bonferroni adjusted alpha. I will examine mean differences for the different dependent variables (outcomes) at 1-month follow-up controlling for the baseline score on the outcome. As covariates, we will also include any demographic variable(s) on which baseline differences are evident in any of the outcomes variables. We will assess whether interventions are significantly different for outcomes at the follow-up point. I will be sensitive to distributional assumptions and will incorporate negative binomial or alternative distributional specifications as appropriate. My first aim focuses on intervention effects on smoking motivation (motivation, confidence, intention to quit and perceived barriers for quitting) as primary dependent variables. My second arm focuses on intervention effects on behavior outcomes (smoking rate, quit attempts, reinforcing nature of smoking, and coping-oriented smoking) as primary dependent variables. My third aim focuses on intervention effects on AS, anxiety/depressive symptoms, and willingness to use coping strategies as primary dependent variables. These criterion variables were selected on the basis of their theoretical and clinical relevance to the study questions and utility. Intervention condition will be included as a dummy coded contrast. Lastly, I will follow the procedures described by MacKinnon and colleagues to assess hypothesized mediation effects of decreased positive expectancies and perceived smoking norms for continued smoking; whereby, path A is the effect of the predictor on the mediator, path B is the effect of the mediator on the outcome, path C is the effect of the predictor on the outcome, and path C' is the effect of the predictor on the outcome controlling of the mediator. All mediation analyses will be temporally ordered such that mediators will be assessed immediately post-intervention and outcomes will be assessed at a later time point than the mediators; baseline scores for mediators and outcomes will be controlled for in mediation analyses. Mediation analyses will be conducted using bootstrapping techniques through PROCESS, a conditional modeling program that utilizes an ordinary least squares-based path analytical framework to test for both direct and indirect effects. An indirect effect is assumed to be significant if the product of paths A and B is significant.

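### Gender stratifies the randomisation, but no outcome or mediation model is committed to including it

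*Combined protocol and SAP*

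**What the plan says.** Gender appears once in the combined protocol and SAP, in the RCT Procedure section: "Based on permuted block randomization by gender, the participant will complete either the (a) PFI or (b) smoking information control". I read this as permuted blocks within gender strata. Block size and allocation ratio are not given.

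The Statistical Analysis Plan section builds the main-effect models from three elements:

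- treatment: "Intervention condition will be included as a dummy coded contrast";
- the baseline value: "I will examine mean differences for the different dependent variables (outcomes) at 1-month follow-up controlling for the baseline score on the outcome";
- a conditional rule for anything further: "As covariates, we will also include any demographic variable(s) on which baseline differences are evident in any of the outcomes variables".

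For mediation it says that "baseline scores for mediators and outcomes will be controlled for in mediation analyses" and does not repeat the demographic rule. Nowhere is the stratification factor assigned to a model.

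**The concern.** A factor used to restrict the randomisation would normally be in the analysis model whatever the data show. Here its inclusion rests on a rule that does not define when a difference counts as evident and does not say which groups are compared. It can be read in two ways:

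- **Arms differ on the demographic.** Stratified blocking balances gender by design, so the rule would almost never pick it up.
- **Demographic groups differ on a baseline outcome.** Gender then enters or stays out according to the observed baseline data and the analyst's choice of threshold.

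Two things are at stake. The first is pre-specification: either model could be defended after the data are seen. The second is precision. When arms are balanced within gender and gender predicts the outcome, omitting it leaves its variance in the residual. The standard error of the treatment contrast is then too wide, and the trial gives up whatever precision the stratification could have bought.

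**Working it through.** **Inputs from the documents.** Planned enrolment is 130 (Recruitment). The primary approach is "examining mean differences between the intervention and control group using general linear mixed modeling". The plan will "correct for alpha inflation using Bonferroni adjusted alpha", but the base alpha, sidedness and number of tests are not stated. The three aims list 4 + 4 + 3 = 11 primary outcomes, or 12 if anxiety and depressive symptoms are counted separately. The documents give no power, effect size or gender-outcome association, so there is no figure of the plan's own to reproduce.

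**Assumptions.** Two-sided alpha 0.05 before correction, 1:1 allocation, equal gender split, complete follow-up, and p<0.05 as the meaning of an evident difference. R² is varied from 1% to 10%.

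**1. Selection if the rule concerns arm imbalance.** With block size b, the arms can differ by at most b/2 within a gender. Even at b = 8 that is 4 people. With about 65 per arm, the difference in proportions is at most about 4/65 = 0.06, against a standard error of √(0.5 × 0.5 × 2/65) = 0.088, so z is about 0.7. Simulation agrees: gender was selected in 0 of 20,000 trials at each of block sizes 4, 6 and 8.

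**2. Selection if the rule concerns baseline outcome differences.** If gender explains a share R² of a baseline outcome, the standardised difference is d = 2√(R²/(1−R²)). The second column below is the power of a t-test with 65 per gender. The rule is triggered by a difference on any outcome, so the last column adds ten independent outcomes unrelated to gender: 1 − (1 − p) × 0.95¹⁰, where 0.95¹⁰ = 0.599.

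| Baseline R² | d | Selected, one outcome | Selected, one related + ten unrelated |
|---|---|---|---|
| 1% | 0.20 | 21% | 52% |
| 2% | 0.29 | 37% | 62% |
| 5% | 0.46 | 74% | 84% |
| 10% | 0.67 | 97% | 98% |

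If gender is unrelated to all 11 outcomes, chance selection runs from 5% (fully correlated outcomes) to 1 − 0.95¹¹ = 43% (independent outcomes).

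**3. Cost of leaving gender out of a linear model.** Here R² is the share of outcome variance that gender explains after baseline adjustment. The reported standard error is too large by a factor 1/√(1−R²), so:

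- type I error = 2[1 − Φ(z/√(1−R²))];
- power = 1 − Φ(z/√(1−R²) − (z + 0.8416)), for an effect with 80% power when gender is included.

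Worked case, R² = 10% and alpha 0.05: z/√0.9 = 1.960/0.949 = 2.066. Type I error is 2[1 − Φ(2.066)] = 0.039. Power is 1 − Φ(2.066 − 2.802) = 76.9%.

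| Residual R² | Type I error (nominal 0.05) | Power, alpha 0.05 | Power, 0.05/4 = 0.0125 | Power, 0.05/11 |
|---|---|---|---|---|
| 1% | 0.049 | 79.7% | 79.7% | 79.6% |
| 2% | 0.048 | 79.4% | 79.3% | 79.2% |
| 5% | 0.044 | 78.5% | 78.1% | 77.9% |
| 10% | 0.039 | 76.9% | 76.0% | 75.4% |

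At these R² values, 0.05/12 gives the same figures as 0.05/11 to this precision.

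**4. Simulation check.** With N = 130, block size 4, condition and baseline score in the model, and 20,000 trials, type I error without gender was 0.049 / 0.048 / 0.045 / 0.039 across the four R² values. With gender it was 0.050 / 0.050 / 0.051 / 0.049.

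A separate simulation at R² = 10% gave power of 77.7% with gender never entered, 79.5% with gender entered by the baseline-outcome reading applied to one outcome, and 80.7% with gender always entered. Simulation error was about 0.9 points.

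**The case against.** The strongest reply is that the planned analysis is valid as written. Type I error never exceeds nominal in the linear scenarios, the treatment contrast is unbiased, and the documents give no evidence that gender predicts any outcome. At R² of 1% to 2% the power loss is 0.3 to 0.8 points across the alphas considered, and there is no stated power target to fall short of. All of this stands, and it limits the point to a modest improvement.

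A second reply is that the rule, read as differences on any baseline outcome, often brings gender in when it matters most. This also stands in part. The one-outcome probabilities are the low end, as the last column of the selection table shows. As a rough illustration, set baseline and residual R² equal, although they are different quantities. Multiplying each loss by the one-outcome probability of non-selection then gives an expected loss of about 0.1 to 0.4 points at alpha 0.05 (for example 1.5 × 0.26 = 0.4) and at most about 0.6 at 0.05/11. But the plan does not commit to this reading. On the other one gender is effectively excluded, and on neither is inclusion assured.

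Third, the negative binomial and bootstrapped mediation models were not quantified, and the mediation sentence does not say that its covariates are the only ones. That is accepted: no gain is claimed for those models.

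**Conclusion.** The point holds. Gender is the randomisation stratum, no model is committed to including it, and its only stated route into the main-effect models is an undefined, data-dependent rule. That gap in pre-specification exists whether or not gender is prognostic.

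The statistical cost is small and conditional. There is no bias, no false-positive inflation, and no loss if gender is unrelated to outcome. Otherwise there is a mildly conservative test and a power loss of 0.3 to 3.1 points at alpha 0.05, up to 4.6 points under Bonferroni over 11 outcomes, for an assumed residual R² of 1% to 10%. These figures apply only to linear models that omit gender. Apart from the planned enrolment of 130 and the outcome count, every input is an assumption. The change is worth making because it costs almost nothing, not because validity is threatened.

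**What to change.** Add one sentence to the Statistical Analysis Plan: every main-effect and mediation model will include gender, the randomisation stratum, as a fixed covariate alongside the baseline score or scores, regardless of any observed baseline differences and independently of the demographic-covariate rule. For the negative binomial and mediation models the justification is consistency with the randomisation.

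The cost is that sentence and one degree of freedom. Gender is already recorded for allocation.

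This settles the matter for gender only. The demographic rule stays undefined for every other variable, and the same edit could usefully remove it or state its comparison groups and threshold.

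### Holm's step-down procedure should replace single-step Bonferroni for the 11 or 12 unranked primary outcomes: same family-wise guarantee, never fewer rejections

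*Combined protocol and SAP*

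**What the plan says.** The Statistical Analysis Plan section of the combined protocol and SAP gives the multiplicity rule in one sentence: "I will employ an intent-to-treat design and correct for alpha inflation using Bonferroni adjusted alpha". Three groups of outcomes are then declared primary:

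- Aim 1: "smoking motivation (motivation, confidence, intention to quit and perceived barriers for quitting) as primary dependent variables", four outcomes.
- Aim 2: "behavior outcomes (smoking rate, quit attempts, reinforcing nature of smoking, and coping-oriented smoking) as primary dependent variables", four outcomes.
- Aim 3: "AS, anxiety/depressive symptoms, and willingness to use coping strategies as primary dependent variables", three outcomes, or four if anxiety and depressive symptoms are tested separately.

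No outcome is placed ahead of another, and no testing order, gatekeeping or step-down rule appears. The section does not state the overall alpha, the divisor, or whether the correction applies within each aim or across all three. There are two arms and one tested follow-up time (1 month), so each outcome yields one p-value. On sample size, the Recruitment section says only that "we will easily be able to enroll 130 participants over a 60-week period".

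**The concern.** In its ordinary meaning, a Bonferroni-adjusted alpha holds every test at alpha divided by the number of tests, however many of the other tests have already succeeded. Holm's procedure starts at the same threshold and relaxes it after each rejection. Both guarantee the same family-wise error bound, and neither needs an assumption about how the outcomes are correlated.

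With about 130 participants and up to 12 primary outcomes, power per outcome matters. The intervention addresses several of these outcomes directly (barriers, coping-related smoking, anxiety sensitivity, coping strategies). If it works as intended, several effects will be real together, and that is where single-step Bonferroni loses most. What is at stake is real effects missed on the second and later outcomes. False positives are already controlled.

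**Working it through.** **Inputs from the document.** Outcomes: 4 + 4 + 3 = 11, or 4 + 4 + 4 = 12. One contrast per outcome. 130 participants.

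**Assumptions, because the document gives no figure.** Family-wise alpha 0.05, two-sided; 1:1 allocation, so 130/2 = 65 per arm; standardised differences d of 0.5 and 0.3; correlation of 0.3 between outcomes; no loss to follow-up; unadjusted two-sample t-tests. The last four are varied below or under the objection. The plan states no threshold or power, so there is no figure of its own to reproduce.

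**Thresholds.** Bonferroni tests every outcome at 0.05/m:

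- m = 3: 0.0167
- m = 4: 0.0125
- m = 11: 0.0045
- m = 12: 0.0042

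Holm compares the i-th smallest p-value with 0.05/(m − i + 1) and stops at the first failure. For m = 4 the sequence is 0.0125, 0.0167, 0.025, 0.05. For m = 12 it runs from 0.0042 up to 0.05.

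**Why Holm cannot do worse.** Its first threshold equals Bonferroni's and each later one is larger, so every Bonferroni rejection is also a Holm rejection. Because the first steps are identical, so is the chance of at least one rejection.

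**Bonferroni power per outcome.** Exact two-sample t-test, 128 degrees of freedom, noncentrality d × √(65/2), which is 2.85 at d = 0.5 and 1.71 at d = 0.3:

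| Alpha per test | d = 0.5 | d = 0.3 |
|---|---|---|
| 0.0167 (m = 3) | 0.664 | 0.241 |
| 0.0125 (m = 4) | 0.625 | 0.209 |
| 0.0045 (m = 11) | 0.487 | 0.124 |
| 0.0042 (m = 12) | 0.476 | 0.119 |

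**Holm against Bonferroni.** Average power per real effect, from 20,000 simulated trials per scenario with participant-level correlated normal data:

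| Outcomes | Real effects | d | Bonferroni | Holm |
|---|---|---|---|---|
| 4 | 1 | 0.5 | 0.63 | 0.63 |
| 4 | 2 | 0.5 | 0.62 | 0.65 |
| 4 | 3 | 0.5 | 0.63 | 0.68 |
| 4 | 4 | 0.5 | 0.62 | 0.72 |
| 12 | 4 | 0.5 | 0.48 | 0.49 |
| 12 | 6 | 0.5 | 0.48 | 0.51 |
| 12 | 8 | 0.5 | 0.48 | 0.53 |
| 12 | 12 | 0.5 | 0.48 | 0.59 |
| 4 | 4 | 0.3 | 0.21 | 0.25 |
| 12 | 12 | 0.3 | 0.12 | 0.14 |

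No simulated trial had a Bonferroni rejection that Holm missed.

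**Sensitivity.**

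- Correlation 0, 0.3 and 0.6 (100,000 replicates), all effects real at d = 0.5: the gain was 11.0, 10.0 and 8.9 points with 4 outcomes, and 10.9, 11.4 and 11.2 with 12.
- 20% loss (65 × 0.8 = 52 per arm), d = 0.5, all real: 0.50 to 0.60 with 4 outcomes and 0.35 to 0.44 with 12. With half real: 0.50 to 0.53 and 0.36 to 0.39.

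**Error rate.** With no real effects the two procedures had identical family-wise error. With 3 of 4 effects real at d = 0.5 it was 0.011 under Bonferroni and 0.031 under Holm. Holm uses more of the permitted error but stays within 0.05.

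**The case against.** The strongest reply is that nothing in the plan is wrong. Bonferroni is valid, and an investigator whose analysis is framed around mean differences may prefer it for its simple simultaneous intervals. That preference is legitimate, but the plan does not state it or say that such intervals will be reported.

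Second, the larger gains need most effects to be real and of moderate size, against a time-matched control that receives the same smoking information. With half the effects real at d = 0.3, power moves only from 0.211 to 0.220 (4 outcomes) and from 0.118 to 0.125 (12). At d = 0.2 with all real it moves from 0.085 to 0.096 and from 0.041 to 0.044. This stands: under those conditions the change hardly matters. It still costs no error control.

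Third, the figures use unadjusted t-tests, while the plan adjusts for baseline and allows negative binomial models. This also stands as a caveat on absolute power. With an assumed baseline correlation of 0.6 and d = 0.5, Bonferroni power is about 0.85 (4 outcomes) or 0.74 (12). The gain remains: with all effects real, Holm reaches about 0.92 and 0.87.

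Fourth, the undefined family matters more in the unadjusted figures. Moving from 4 to 12 outcomes lowers Bonferroni power at d = 0.5 from 0.625 to 0.476, about 15 points, which exceeds any Holm gain in the table above. That is a reason to name the family in the same edit. It is not a reason to keep single-step Bonferroni.

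**Conclusion.** The concern holds, as an improvement in efficiency and not as an error in the plan. That Holm rejects at least as much as Bonferroni at the same family-wise bound is a mathematical result that needs no assumption about effect sizes or correlation. The size of the benefit does rest on the assumptions listed above. At d = 0.5 it is 0 to 3 points of average power when half or fewer effects are real, about 5 when two thirds to three quarters are, and 10 to 11 when all are. At d = 0.3 with all real it is 2 to 4 points. The chance of at least one positive primary outcome is the same under both methods. Reading the plan as single-step is an inference, but it is the ordinary meaning of its words.

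**What to change.** In the Statistical Analysis Plan section, replace the Bonferroni clause with wording such as: *Holm's step-down procedure at the same family-wise alpha, applied to [family], with the outcomes in the family listed.*

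The sponsor should complete it with:

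- the overall alpha and the family already intended, per aim or study-wide. If study-wide was meant it should stay so, because moving to per-aim families would widen the study-wide error;
- whether anxiety and depressive symptoms count as one outcome or two;
- whether the correction also covers the indirect effects in the mediation analyses. The text can be read either way and does not list the mediator–outcome pairs, so no error rate is claimed for them here.

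The cost is SAP wording only. Design, sample size and data collection do not change, and Holm needs only the p-values the planned models already give, including any from negative binomial models. There are two downsides. Simultaneous confidence intervals that match Holm are less simple than Bonferroni's, and the realised family-wise error sits closer to its limit when some effects are real, though never above it.

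### The mediation models adjust only for baseline mediator and outcome scores and plan no sensitivity analysis, leaving path B open to a shared cause

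*Combined protocol and SAP*

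**What the plan says.** The relevant text is in the Statistical Analysis Plan, in the paragraph on the primary analyses.

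- The main strategy has two parts: comparing arm means, and "evaluating expectancies and norms as mediators of intervention effects".
- The mediation hypotheses concern "hypothesized mediation effects of decreased positive expectancies and perceived smoking norms for continued smoking".
- On timing, "mediators will be assessed immediately post-intervention and outcomes will be assessed at a later time point than the mediators".
- On covariates, "baseline scores for mediators and outcomes will be controlled for in mediation analyses". No other covariate is named for the mediation models.
- The models are ordinary least squares path models with a bootstrap. The decision rule reads: "An indirect effect is assumed to be significant if the product of paths A and B is significant".

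One further covariate rule appears earlier, with the between-arm comparisons: "As covariates, we will also include any demographic variable(s) on which baseline differences are evident in any of the outcomes variables". It is not repeated for mediation, and it covers demographic variables only.

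Under RCT Procedure, allocation is described as "Based on permuted block randomization by gender". The section on the personalised intervention shows that nicotine dependence and AS are scored to build the feedback, and it describes a link between smoking and AS. No section states an assumption of no mediator-outcome confounding or plans an analysis to probe it.

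**The concern.** Only condition is randomised. That makes the effect of condition on the mediator (path A) a randomised comparison. The relation of the mediator to the outcome (path B) is between two observed variables, and anything that drives both will appear in it.

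Two features of the plan help. Measuring the mediator before the outcome guards against reverse causation, though not against a shared cause. Adjusting for both baseline scores absorbs part of a stable shared cause, but not one that acts after baseline, nor the part of a trait that the baseline scores do not capture.

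The conclusion about mechanism is what is at stake. The plan defines path B as an effect of the mediator and judges mediation by the significance of A x B alone. A reader of the results would have no indication of how little residual confounding could account for a significant product.

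**Working it through.** The documents give no power figure, effect size or mediation estimate, so there is no stated figure to reproduce. The check asks how often the planned test declares mediation when there is none.

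**Inputs from the documents.** N = 130 (Recruitment); covariates are the two baseline scores; the test is a bootstrap of A x B in least squares models (Statistical Analysis Plan).

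**Assumed inputs.** 1:1 arms; complete follow-up; residual SD 1 for mediator and outcome; baseline correlation 0.3; true path B = 0; path A of 0 to 0.6 SD; residual mediator-outcome correlation rho of 0.1 or 0.2 after the planned adjustment. Alpha is 0.05, or 0.05/11 if the Bonferroni correction reaches mediation and its family is the 4 + 4 + 3 = 11 outcomes of the three aims (anxiety/depressive symptoms counted once).

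**Step 1: the bias.** With true B = 0 and residual SDs of 1, the fitted path B estimates rho, so A x B estimates A × rho. For A = 0.6 this is 0.6 × 0.1 = 0.06 or 0.6 × 0.2 = 0.12. For A = 0 it is zero.

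**Step 2: hand approximation.** Treat A x B as significant when both paths are.

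- Path A: SE = 2/√130 = 0.175, so A = 0.6, 0.3 and 0.2 give ratios of 3.42, 1.71 and 1.14. The probability of significance at alpha 0.05 is 0.92, 0.40 and 0.20 (and 0.05 at A = 0).
- Path B: degrees of freedom are 130 − 5 = 125, and the ratio is rho × √125/√(1 − rho²), which is 1.12 at rho = 0.1 and 2.28 at rho = 0.2. The critical value is 1.979, so the probability of significance is 0.20 and 0.62.
- Products, for example: 0.92 × 0.20 = 0.18 and 0.92 × 0.62 = 0.57.

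**Step 3: simulation of the planned analysis.** Percentile bootstrap of A x B with both baseline scores as covariates. Ranges span repeated runs of at least 600 simulated trials (Monte Carlo SE at most about 2 points).

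| Path A | rho 0.1, hand | rho 0.1, simulated | rho 0.2, hand | rho 0.2, simulated |
|---|---|---|---|---|
| 0.6 | 18% | about 20% | 57% | 55–59% |
| 0.3 | 8% | 7–9% | 25% | 21–22% |
| 0.2 | 4% | about 4% | 13% | 10–11% |
| 0 | 1% | at most 3% | 3% | at most 3% |

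With rho = 0 and path A = 0.6 the simulated rate is 5%, so the test itself behaves. At 0.05/11 and path A = 0.6 the rates are about 3–5% (rho 0.1) and 21–23% (rho 0.2); at path A = 0.3 they are about 1% and 3%.

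**Step 4: how strong is rho?** A single shared cause equally related to both variables needs a partial correlation of √rho with each: √0.1 = 0.32 or √0.2 = 0.45. The second is strong confounding.

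**Step 5: do baseline scores remove a stable trait?** Take a trait U (variance 1) loading L on all four scores, with no other carry-over from baseline. Given both baselines, Var(U) = 1/(1 + 2L²/(1 − L²)). For L = 0.5 this is 0.60, leaving a residual covariance of 0.25 × 0.60 = 0.15, a residual variance of 0.75 + 0.15 = 0.90, and rho = 0.15/0.90 = 0.17. For L = 0.7 the same steps give rho = 0.168/0.678 = 0.25. Simulated with path A = 0.5, these trials gave 41% and 75% false findings after the planned adjustment, and 4% and 6% with the trait itself in the model.

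**The case against.** The strongest reply is that the large percentages need a large path A. This stands. A shared cause inflates A x B only when condition really moves the mediator. The two arms are time matched and share the smoking information content, so a small shift is plausible. At path A = 0.2 even strong confounding gives only 10–11%.

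A second reply is that the plan already has protection in its time ordering and baseline adjustment. This stands in part, and how much confounding remains depends on the model. If the baseline score itself carries over with coefficient 0.3 and the trait loading is 0.5, about 0.097 remains, rather than the 0.17 found above without carry-over.

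A third is that the proposed covariates are not shown to work. This also stands. That dependence and AS drive both mediator and outcome is plausible but assumed. In the carry-over example, adding a covariate correlated 0.5 or 0.7 with the trait lowers 0.097 only to 0.082 or 0.064. Gender has a design reason for inclusion, as the stratifier, but that does not show that it confounds path B.

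A reader might infer that a significant A x B can never be told apart from a shared cause, or that the bootstrap test is invalid. The documents support neither. The test is sound for the statistical indirect effect, and the plan's safeguards have some value. A reader might also take the demographic covariate rule or the Bonferroni statement ("correct for alpha inflation using Bonferroni adjusted alpha") as settling the matter. Both are stated with the between-arm comparisons. The first could bring in gender, but not dependence or AS. Whether the second covers mediation is not said, and it would lower the rates without removing the bias.

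**Conclusion.** The point holds in a limited form. The plan gives mediation a main role, adjusts only for baseline mediator and outcome scores, and leaves the no-confounding assumption behind path B unstated and untested. If the intervention shifts the mediator and a shared cause remains, the planned test can report mediation where there is none. The size runs from no inflation (path A zero) to more than half of trials (path A 0.6, rho 0.2). These figures rest on assumed effect sizes, so the range carries the argument rather than any single entry.

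The three aims' randomised comparisons are not affected. Whether to fit the two mediators jointly, and which alpha applies to mediation, are separate optional questions and not part of this point. This is a modest but worthwhile correction to what the mediation analysis may claim.

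**What to change.** 1. Add to the mediator and outcome models gender (the randomisation stratifier), baseline nicotine dependence, and baseline AS where it is not already the outcome baseline. This assumes that both arms supply dependence and AS in the pre-intervention survey. How much confounding it removes cannot be known from the documents.
2. Pre-specify a sensitivity analysis of A x B over the residual mediator-outcome correlation, for example −0.3 to 0.3. With r the mediator-outcome residual correlation given condition and covariates, and sY and sM the corresponding residual SDs, use B(rho) = (sY/sM) × [r − rho × √((1 − r²)/(1 − rho²))] and bootstrap A × B(rho). Report the rho at which the effect reaches zero (for this formula, rho = r) and the rho at which the interval first includes zero.
3. Describe a significant A x B as consistent with mediation, assuming no unmeasured mediator-outcome confounding.

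The cost is up to 3 of about 125 degrees of freedom, a short extra analysis of the same fitted models, and a more cautious mediation statement. No new data are needed under the survey assumption above.

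The sensitivity analysis grades the evidence without settling it. In simulation at path A 0.6 and alpha 0.05, allowing rho = 0.10 brought zero into the interval for 91% of spurious findings when the true rho was 0.1 and for 65% when it was 0.2. It also did so for 34% of findings when path B was truly 0.3.
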